Results from a phase II (PEAK) and a phase III (FIRE-3) randomized trials comparing a chemotherapy doublet plus an anti-EGFR with a chemotherapy doublet plus the anti- Vascular Endothelial Growth Factor bevacizumab suggest that the upfront use of the anti-EGFR may be beneficial for *RAS* wild-type patients in terms of overall survival, thus further supporting the adoption of these regimens as first-line choices. These findings have not been confirmed by another phase III trial (CALGB80405) showing no significant differences between a chemotherapy doublet (mainly FOLFOX) plus cetuximab or bevacizumab in terms of OS. A higher response rate was however reported in the chemotherapy plus cetuximab group. Based on these results both chemotherapy plus an anti-EGFR or chemotherapy plus bevacizumab are valid options as upfront treatment for mCRC patients. The choice will be mainly based, on a case-by-case basis, on the treatment's objective and on patients' expectations. To this regard, the impact of the treatment on patients' quality of life, that is tightly connected to the management of occurring adverse events, as well as physicians' confidence with these regimens will be of crucial importance.

In Italy two anti-EGFR MAbs are currently approved for the treatment of adult patients with wild-type *RAS* metastatic colorectal cancer.

Panitumumab is indicated for the treatment of adult patients with wild-type *RAS* metastatic colorectal cancer:

- in first-line in combination with FOLFOX or FOLFIRI;
- in second-line in combination with FOLFIRI for patients who have received first- line fluoropyrimidine-based chemotherapy (excluding irinotecan);
- as monotherapy after failure of fluoropyrimidine, oxaliplatin, and irinotecan containing chemotherapy regimens.

Approved

Cetuximab is indicated for the treatment of patients with epidermal growth factor receptor (EGFR)-expressing, *RAS* wild-type metastatic colorectal cancer:

in combination with irinotecan-based chemotherapy;

in first-line in combination with FOLFOX;

as a single agent in patients who have failed oxaliplatin- and irinotecan-based therapy and who are intolerant to irinotecan.

Dermatologic adverse events of any grade are observed in more than 90% of patients treated with panitumumab and appropriate dose reductions and delays are suggested in the case of skin symptoms  $\geq$  G3 according to the NCI CTCAE classification.

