## 8.2 Secondary

To investigate the impact of dermatological adverse events during the treatment with FOLFOX or FOLFIRI plus anti-EGFR MAbs on patients' skin satisfaction as measured by means of the Dermatology Life Quality Index (DLQI) questionnaire.

To assess the tolerability of administered treatments.

To describe the adherence to the treatment in terms of dose delays, dose reductions, number of administered cycles, average relative dose intensity of every drug.

To describe the management of dermatological adverse events.

To assess the effect on skin-related QoL of preemptive vs reactive treatment of skin toxicities.

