## 9. Research Methods

### 9.1 Study Design

This is a national, multicentric, prospective, observational trial. The decision to prescribe FOLFOX or FOLFIRI plus panitumumab or FOLFOX or FOLFIRI plus cetuximab must have been freely taken by the clinician prior to the study entry for each patient included. Each physician will see his/her patients within the context of routine visits, without any special visit being organized for the purposes of the study. Therefore, the doctor-patient relationship and patient follow-up are not modified. Physicians are totally free to decide on their patients' therapeutic management.

EORTC QLQ-C30 and DLQI questionnaires will be completed by the patients at baseline (Day 1 of Cycle 1), at the first day of every other cycle (every 2 weeks) thereafter, and at "End of Study Visit" (within 28 days from the end of treatment with anti-EGFR or withdrawal from study for any reason).

Before every cycle, adverse events will be recorded and graded according to NCI CTCAE Version 4.0. Treatment's modifications in terms of cycles' delay, dose reductions or drugs' interruptions will be recorded. Concomitant approaches to prevent or treat dermatological toxicities during the treatment will be registered.

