### 9.3.3 Covariate Assessment

*Not applicable*

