## 9.5 Study Size

Generally the impact of treatments on cancer patients' QoL is explored in clinical studies as a marginal aspect: data are not collected systematically and no longitudinal information are available about this aspect. So, no evidence of outcomes is present in literature.

For the above reasons the study sample size is not based on mathematical or hypothesis evaluations, or power estimation, but on feasibility considerations.

- Expected number of subjects presenting selected diseases and respecting inclusion/exclusion criteria
- Enrolment capacity and management of patients from centers
- Number of patients with the same disease enrolled in other studies, and their mean follow up time observed

A total sample size of 300 patients has been planned for this study: it is estimated that about 50% (150 pts) of them should be able to complete the QoL questionnaires during the whole treatment period. This population is estimated relevant from the scientific board and useful for a first evaluation on variability of QoL during the whole treatment period.

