#### **9.7.2.1 General Considerations**

All recorded parameters will be described: absolute frequency and percentage will be calculated for qualitative variables, while mean, standard deviation, median, first and third quartile will be used to summarize quantitative variables.

The population will be analyzed totally and stratified for treatment (FOLFOX plus panitumumab and FOLFOX plus cetuximab).

The level of significance will be set to  $p < 0.05$ . No interim analyses are planned for this study.

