#### **9.7.2.4 Analysis of the Primary, Secondary, and Exploratory Endpoint(s)**

To reach the primary endpoint ("To assess the impact of the treatment with FOLFOX or FOLFIRI plus anti-EGFR MAbs on patients' health related quality of life"), comparison between the QoL scores (total and partials) at different times will be done and

differences in mean from basal and follow-up times will be tested with T-test (Student T-test) paired data.

EORTC-QLQ C30 score will be calculated in the total population and also in the two subgroups: FOLFOX/FOLFIRI plus panitumumab and FOLFOX/FOLFIRI plus cetuximab.

Differences in mean between the two subpopulation will be tested at different times with T-test.

- To investigate the impact of dermatological adverse events during the treatment with FOLFOX or FOLFIRI plus anti-EGFR MABs on patients' skin satisfaction will be calculated the Dermatology Life Quality Index (DLQI) score.

Differences in mean between the two subpopulation will be tested at different times with T-test.

- To assess the tolerability of administered treatments, Tolerability and compliance to treatments will be described. Their effect on QoL will be evaluated with a multivariate analysis (Anova).
- To describe the adherence to the treatment **with antiEGFR** in terms of dose delays, dose reductions, number of administered cycles, average relative dose intensity of every drug, all these parameters will be described and the single values observed will be compared with the values reported previously, to determine variations .
- Every adverse event occurred will be described with particular attention to dermatologic ones: description, severity and management of the event will be illustrated. Correlation with number of event and treatments (FOLFOX/FOLFIRI plus panitumumab and FOLFOX/FOLFIRI plus cetuximab) will be verify with a multivariate analysis (Anova)
- Will be verified the presence of preemptive treatment of skin toxicities, and events of skin toxicities . The correlation between events of skin toxicities, QoL and presence of preemptive treatment will be tested with a multivariate analysis (Logistic)

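### The preemptive-versus-reactive skin-care analysis names no confounder, although prophylaxis is the physician's choice and the objective asks for an effect on skin-related quality of life

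*Combined protocol and SAP*

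**What the plan says.** All references are to the combined protocol and SAP.

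- **Objective (8.2):** "To assess the effect on skin-related QoL of preemptive vs reactive treatment of skin toxicities".
- **Analysis (9.7.2.4, last bullet):** "The correlation between events of skin toxicities, QoL and presence of preemptive treatment will be tested with a multivariate analysis (Logistic". Three quantities are named. The text does not say which is the outcome, whether QoL means DLQI or QLQ-C30, or at which time QoL is taken.
- **Who gets prophylaxis (9.1):** "Physicians are totally free to decide on their" patients' management, so prophylaxis is not allocated by the study.
- **Confounding:** 9.3.3 (covariates), 9.7.2.5.2 (stratified analysis) and 9.7.2.5.3 (residual confounding and bias) are each marked not applicable. The bias statement in 9.9.1 concerns sequential recruitment, not who among the recruited receives prophylaxis.
- **Stratification (9.7.2.1):** the population is to be analysed in total and by treatment, but only the two FOLFOX regimens are named.
- **Testing:** 7.3 says that analyses are descriptive with no inference, yet 9.7.2.1 states "The level of significance will be set to" p < 0.05, and 9.7.2.4 says this correlation will be tested.
- **Data collected (9.3 and Table 1):** sex, date of birth, medical history and anti-EGFR drug at screening; ECOG, administered chemotherapy and anti-EGFR, prophylaxis (yes/no) and DLQI at baseline. Prophylaxis is recorded again at each study visit. The skin-toxicity assessment starts only at the study visits.

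**The concern.** Patients given prophylaxis may differ from the others before treatment starts. If physicians use it more where they expect worse skin reactions, a crude comparison charges the extra reactions to prophylaxis. If they use it less there, prophylaxis gets undeserved credit. An analysis that names no baseline factor cannot separate either pattern from a real effect.

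Two candidates stand out. One is the anti-EGFR drug: the bullet just before this one in 9.7.2.4 relates event counts to drug, yet the prophylaxis analysis does not name it. The other is the skin condition at the start. The QoL term does not settle the matter. Nothing says it is the baseline value, and on-treatment QoL can itself be changed by prophylaxis, so adjusting for it would not remove confounding.

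At stake is the answer on prevention of skin toxicity, which readers may well carry into practice. Adjusting the separate panitumumab-versus-cetuximab comparison would not repair this one.

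**Working it through.** **The plan's own figure.** 9.5 says "A total sample size of 300 patients has been planned for this study" and "it is estimated that about 50% (150 pts) of them should be able to complete the QoL questionnaires": 300 × 0.50 = 150, which reproduces. No power or effect size is given for this analysis, so there is nothing further to reproduce. Sample sizes of 300 and 150 are used below.

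**Inputs from the documents.** Section 7 gives skin effects in 50-90% for the anti-EGFR class. Section 7.1 says "Dermatologic adverse events of any grade are observed in more than 90% of patients treated with panitumumab".

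**Assumed inputs (not in the documents).** Any skin event in 92% on panitumumab and 75% on cetuximab; prophylaxis in 70% and 30%; equal drug split; no effect of prophylaxis within either drug.

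**Step 1: crude odds ratio with drug as the only confounder.** Let s be the panitumumab share, tP and tC the event rates, and pP and pC the prophylaxis shares.

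- With prophylaxis: r1 = [s·pP·tP + (1−s)·pC·tC] / [s·pP + (1−s)·pC] = 0.7 × 0.92 + 0.3 × 0.75 = 0.869 (at s = 0.5 the weights reduce to 0.7 and 0.3)
- Without: r0 = 0.3 × 0.92 + 0.7 × 0.75 = 0.801
- OR = (0.869/0.131) / (0.801/0.199) = 1.65; the true value is 1.0

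**Step 2: range.** Cetuximab rate 60-85%, prophylaxis 60/40 to 80/20, panitumumab share 50-70%.

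- Low end (share 70%, cetuximab 85%, 60/40): r1 = (0.42 × 0.92 + 0.12 × 0.85)/0.54 = 0.904; r0 = (0.28 × 0.92 + 0.18 × 0.85)/0.46 = 0.893; OR 1.14
- High end (share 65%, cetuximab 60%, 80/20): r1 = (0.52 × 0.92 + 0.07 × 0.60)/0.59 = 0.882; r0 = (0.13 × 0.92 + 0.28 × 0.60)/0.41 = 0.701; OR 3.18
- Prescribing reversed: the two groups swap, so the OR is the reciprocal, 1/1.65 = 0.61 in the main example
- Equal prophylaxis shares, or equal event rates: OR 1.00

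**Step 3: chance of a false p < 0.05 (two-sided assumed).** With panitumumab at 90%, cetuximab at 70% and prophylaxis 70/30, the crude OR is 1.66, and p < 0.05 occurs in 41% of studies at N = 300 and 23% at N = 150.

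**Step 4: drug and baseline skin status together.** Simulation, 2000 runs per scenario and no true effect. Assumed: 50% on each drug, 25% with poor baseline skin, 70% with toxicity overall, 50% given prophylaxis overall. Both factors carry the same odds ratio (OR) in each row.

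| OR for toxicity / for prophylaxis | Crude OR | False positives, no adjustment (N=300 / 150) | Drug only | Drug + baseline skin |
|---|---|---|---|---|
| 2 / 1 | 1.00 | 4.4% / 4.6% | 4.6% / 4.7% | 4.4% / 4.6% |
| 2 / 2 | 1.21 | 12.2% / 9.0% | 6.4% / 5.8% | 5.4% / 4.4% |
| 3 / 3 | 1.54 | 38.8% / 21.1% | 10.8% / 7.8% | 4.2% / 4.8% |
| 3 / one third | 0.65 | 40.8% / 22.0% | 11.0% / 8.4% | 4.9% / 5.2% |

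Adjusting for both restores the nominal 5%. Adjusting for drug alone does not when both links are strong. Baseline skin alone, with both ORs at 2, gives a crude OR of 1.08 and 5% false positives, so a weak link does little harm.

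**The case against.** **The plan already stratifies by drug.** A reader might infer that the drug is left out altogether. The documents do not support that: 9.7.2.1 sets a general stratification by treatment, and if it reaches this analysis, drug confounding disappears within strata. But the text names only FOLFOX regimens, the total-population result stays crude, baseline skin is untouched, and 9.7.2.5.2 calls stratified analysis not applicable. This part of the objection narrows the point without removing it.

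**The model is not closed.** 9.7.2.4 names three quantities in an analysis called multivariate; it does not say that nothing else may enter. True, but 9.3.3 is where covariates would be listed, and it lists none.

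**The premises are not documented.** This stands. The 50-90% in section 7 covers the class, panitumumab included, so setting it against the figure above 90% in 7.1 is not a between-drug contrast, and no cetuximab rate is given. No passage says what guides prophylaxis, and 7.2 says that no Italian data on managing this toxicity exist. The range in step 2 starts at 60/40 and so leaves out the null.

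**Baseline skin status is not recorded as such.** Also correct. Table 1 schedules no skin-toxicity assessment at baseline. Baseline DLQI, medical history and AE/SAE are proxies.

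**The analysis is only descriptive.** 7.3 says so, and 9.7.2.4 speaks of correlation. But 8.2 asks for an effect and a test at 0.05 is planned, so the label gives limited protection.

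**Conclusion.** The concern holds in this form: a non-randomised comparison serving a causally worded objective is to be tested without any prespecified confounder, and 9.7.2.1, 9.7.2.4 and 9.7.2.5.2 disagree on whether it is stratified by drug. The possible bias runs in either direction.

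Its size rests wholly on assumptions. The OR of 1.65, and the range of about 1.1 to 3.2 (reciprocals if prescribing is reversed), require both that skin risk differs by drug and that prophylaxis follows the drug. If either link is absent, drug contributes no bias.

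Two stronger readings should be resisted. A reader might infer that the prophylaxis result will be wrong; the documents show only that the stated analysis could not tell. A reader might also take 1.65 as the error in the answer to objective 8.2. It is not: it concerns the occurrence of any skin event, whereas the objective is skin-related quality of life, and no DLQI bias has been calculated.

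**What to change.** In 9.7.2.4:

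- State the outcome: on-treatment DLQI or its change from baseline, to match objective 8.2. Put skin events in a separate model.
- Define the exposure as prophylaxis recorded at baseline (Day 1), yes versus no.
- Adjust for anti-EGFR drug, chemotherapy backbone, baseline DLQI (named as a proxy for baseline skin status), age, sex and ECOG, or use a propensity score built on these.
- Keep post-baseline QoL out of the adjustment set.
- Report crude and adjusted estimates side by side with 95% confidence intervals, and describe the result as an association.

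List the covariates in 9.3.3 in place of the not-applicable entry. Reconcile 9.7.2.1, 9.7.2.4 and 9.7.2.5.2 on stratification by treatment, including the FOLFIRI regimens.

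Cost: wording only, since every variable is already collected at screening or baseline. The model gains a few parameters, and the interval may be slightly wider. Adjustment reaches only measured factors, which is why the result remains an association.

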#### **9.7.2.5 Sensitivity Analysis**

Not applicable

#### **9.7.2.5.1 Subgroup Analysis**

Not applicable

#### **9.7.2.5.2 Stratified Analysis**

Not applicable

#### **9.7.2.5.3 Sensitivity Analysis for Residual Confounding and Bias**

Not applicable

#### **9.7.2.5.4 Other Sensitivity Analysis**

Not applicable

#### **9.7.3 Analysis of Safety Endpoint(s)/Outcome(s)**

Not applicable

#### **9.8 Quality Control**

Source data verification will be performed at the study site, in accordance with Amgen SOPs.

The Investigator is to maintain a list of appropriately qualified persons to whom he/she has delegated study duties. All persons authorized to make entries and/or corrections on CRFs will be included on the Amgen Delegation of Authority Form. Source documents are original documents, data, and records from which the subject's CRF data are obtained. These include but are not limited to hospital records, clinical and office charts, laboratory and pharmacy records, diaries, microfiches, radiographs, and correspondence.

The Investigator and study staff are responsible for maintaining a comprehensive and centralized filing system of all study-related (essential) documentation, suitable for inspection at any time by representatives from Amgen and/or applicable regulatory authorities.

Elements to include:

- Subject files containing completed CRF, informed consent forms, as applicable, and subject identification list.
- Study files containing the protocol with all amendments, copies of pre-study documentation, and all correspondence to and from the IRB/IEC or other relevant ethical review board and Amgen.

In addition, all original source documents supporting entries in the CRFs must be maintained and be readily available.

Retention of study documents will be governed by the contractual agreement with Amgen.

## **9.9 Limitations of the Research Methods**

### **9.9.1 Internal Validity of Study Design: Information Bias**

Patients will be recruited sequentially from the centers, with no selection: all patients attending to the ambulatory and fulfilling the criteria of inclusion/exclusion will be recruited. This minimizes the introduction of bias.

## **10. Protection of Human Subjects**

### **10.1 Informed Consent**

A copy of the proposed informed consent form is to be submitted to the IRB/IEC for written approval before recruitment of subjects into the study. The written informed consent document is to be prepared in the language(s) of the potential subject population.

Before a subject's participation in the study, the investigator is responsible for obtaining written informed consent from the subject or legally acceptable representative after adequate explanation of the aims, methods, anticipated benefits and before any protocol-specific activities are conducted. A legally acceptable representative is an individual or other body authorized under applicable law to consent, on behalf of a prospective subject, to the subject's participation in the study.

The acquisition of informed consent and the subject's agreement or refusal of his/her notification of the primary care physician is to be documented in the subject's medical records, and the informed consent form is to be signed and personally dated by the subject or a legally acceptable representative and by the person who conducted the informed consent discussion. The original signed informed consent form is to be retained in accordance with institutional policy, and a copy of the signed consent form should be provided to the subject or legally acceptable representative.

If a potential subject is illiterate or visually impaired and does not have a legally acceptable representative, the investigator must provide an impartial witness to read the informed consent form to the subject and must allow for questions. Thereafter, both the subject and the witness must sign the informed consent form to attest that informed consent was freely given and understood.

### **10.2 Institutional Review Board/Independent Ethics Committee (IRB/IEC)**

A copy of the protocol, proposed informed consent form, other written subject information, and any proposed advertising material must be submitted to the IRB/IEC for written approval. A copy of the written approval of the protocol and informed consent form must be received by Amgen before recruitment of subjects into the study.

The investigator must submit and, where necessary, obtain approval from the IRB/IEC for all subsequent protocol amendments and changes to the informed consent document. The investigator is notify the IRB/IEC of deviations from the protocol or serious adverse drug reactions occurring at the site and other adverse event reports received from Amgen, in accordance with local procedures.

### **10.3 Subject/Patient Confidentiality**

The investigator must ensure that the subject's confidentiality is maintained for documents submitted to Amgen.

Subjects are to be identified by a unique subject identification number.

- Where permitted, date of birth is to be documented and formatted in accordance with local laws and regulations.
- On the CRF demographics page, in addition to the unique subject identification number, include the age at time of enrollment.
- Documents that are not submitted to Amgen (eg, signed ICFs) are to be kept in confidence by the investigator, except as described below.

In compliance with Local country regulations/ICH Good Clinical Practice (GCP) Guidelines, it is required that the investigator and institution permit authorized representatives of the company, of the regulatory agency(s), and the IRB/IEC direct access to review the subject's original medical records for verification of study-related assessments and data.

Direct access includes examining, analyzing, verifying, and reproducing any records and reports that are important to the evaluation of the study. The investigator is obligated to inform and obtain the consent of the subject to permit such individuals to have access to his/her study-related records, including personal information.

### **10.4 Subjects Decision to Withdraw**

**Subjects have the right to withdraw from the study at any time and for any reason without prejudice to their future medical care by the physician or at the institution.**

**Withdrawal of consent for a study means that the subject does not wish to or is unable to continue further study participation. Subject data up to withdrawal of consent will be included in the analysis of the study and, where permitted, publicly available data can be included after withdrawal of consent. The investigator is to discuss with the subject appropriate steps for withdrawal of their consent from the study.**

